1 BACKGROUND

On-going and additional clinical benefits of statin therapy after trial completion have been demonstrated to accrue from a number of trials (including the 4S Study¹ and the LIPID Study^{2,3} in secondary prevention patients, and the WOSCOPS Study^{4,5} and ASCOT study⁶ in primary prevention). Furthermore, collectively in all those trials contributing to the Cholesterol Treatment Trialists' Collaboration⁷ with accessible published follow-up data, in patients who received active treatment rather than placebo over (the 3–6 years of) the original trial period, the same pattern of on-going advantage and additional risk reduction is seen.⁸ This is seen despite mostly identical usage rates of lipid-lowering therapy between the original groups for many years after completion of the trials.

In meta-analysis of the trials with accessible published post-trial data, an 8% additional reduction in total mortality at 2 years after trial close, 18% reduction in coronary mortality, and 7% reduction in total mortality and 12% reduction in coronary mortality over the next 5 years after trial close was recently reported.⁸ Collectively, these findings could have a major impact on how early initiation of lipid-lowering treatment should be considered in patients at risk. Also, because of greater emerging absolute risk differences than those apparent immediately at trial end, the net clinical benefits estimated relative to treatment costs becomes more favorable for earlier (vs deferred) intervention attributable to the original treatment assignment.

The same may or may not be true of PCSK9 inhibitor therapy, and so this needs to be examined prospectively and systematically. Similarly, in terms of potential safety issues, longer-term data after exposure provides more reliable evidence about the safety of therapy intended to be used for many years.

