2 AIM AND OBJECTIVES

The aim of this study is to determine potential long-term effects on cardiovascular outcomes of evolocumab treatment in patients enrolled in the FOURIER OUTCOMES trial through extended follow-up of selected participants beyond the treatment period.

The **primary objective** is to evaluate potential long-term effects of evolocumab treatment on a composite of CV death, MI, stroke or coronary revascularization in patients completing participation in the FOURIER OUTCOMES trial over a period of up to 5 years following completion of the FOURIER OUTCOMES trial.

The **secondary objectives**, each over a period of up to 5 years following completion of the FOURIER OUTCOMES trial, are:

1. To evaluate the long-term effect of evolocumab treatment on CV death, MI and stroke.
2. To evaluate the long-term effect of evolocumab treatment on CV death.
3. To evaluate the long-term effect of evolocumab on CHD death.
4. To evaluate the long-term effect of evolocumab treatment on the individual components of the primary endpoint and any other cardiovascular hospitalizations.
5. To evaluate the long-term effect of evolocumab treatment on amputation and peripheral revascularization.
6. To evaluate the long-term effect of evolocumab treatment in terms of all-cause death (and non-CV, including cancer, death).

Two exploratory analyses will be performed:

1. To assess effect modification of use of prescription lipid-lowering treatment classes (statins, cholesterol absorption inhibitors, PCSK9i) administered at FOURIER OUTCOMES trial entry on the outcomes above.
2. To assess the effect modification by baseline characteristics on defined study outcomes above.

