9 STATISTICAL CONSIDERATIONS

9.1 Sample Size

The event rate for the primary endpoint in the parent FOURIER OUTCOMES trial among participants allocated to placebo was 11.3% over a median follow-up of 2.2 years (i.e., 5% per annum). For a minimum of 10,000 participants, followed over 5 years post-trial, with an assumed average post-trial event rate of 5% per annum for the primary endpoint excluding hospitalization for unstable angina pectoris (UAP), then the observational FOURIER LEGACY study would have over 95% power at $2P=0.05$ to detect an additional 20% proportional event reduction accruing post-trial, and over 90% power to detect an additional 15% proportional event reduction. The study would also offer 80% power at $2P=0.05$ to detect a 23% reduction in CVD death from 4.94% to 3.8% over up to 5 years.

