9.2 Statistical Analysis

The analyses will examine the effects of long-term evolocumab therapy on cardiovascular events, total mortality, and cause-specific mortality. Analyses will include all participants who entered the FOURIER LEGACY study in participating countries, irrespective of whether they completed the FOURIER LEGACY study. (Data including baseline characteristics, medications, event history and during follow-up etc. will be incorporated into the follow-up database from the FOURIER OUTCOMES trial database). The characteristics of participants at participating sites/countries who did and did not contribute to the FOURIER LEGACY study will be compared. Likewise, the characteristics of subjects who complete the FOURIER LEGACY study vs. those who do not will be compared.

Qualitative and quantitative data will be described using counts, means, medians, and percentages with ranges or standard deviations as appropriate. Event data will be analyzed according to the participants' original randomly assigned therapy in the OUTCOMES study, on an intention-to-treat basis. Time to event information will be presented using Kaplan-Meier curves, and described according to Cox proportional hazard ratios (and 95% CIs), with comparisons between curves using standard log-rank tests. Similar methodology will be used for analyses of any pre-specified subgroups (e.g., baseline participant characteristics). In the circumstance that the hazards violate the test of proportionality, methods such as time-partitioned regression techniques will be utilized. Tests for interaction will be used to evaluate for evidence of differences in treatment effects between subgroups. Recurrent event analysis will be performed using the methods of Wei, Lin and Weissfeld¹². Analyses, both unadjusted and adjusted for baseline measures, will be performed. Cause-specific mortality will also be analyzed using competing risks methods.

Further analysis investigating the impact of baseline characteristics (at time of randomization into the OUTCOMES study) on events will be performed using regression methods (linear, logistic, and proportional hazards) as appropriate.

Separate analyses examining effects post study close will be performed to evaluate the trajectory of effects long-term using appropriate methods (e.g., landmark analysis and conditional probability plots), again by original treatment assignment, among the FOURIER LEGACY study cohort from the time of randomization.

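### Per-arm Kaplan-Meier curves would modestly overstate 5-year incidence for endpoints that leave out some deaths; Section 9.2 names competing-risks methods for cause-specific mortality alone

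*Protocol*

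**What the plan says.** Protocol Section 9.2 sets the general display and comparison for event data: "Time to event information will be presented using Kaplan-Meier curves, and described according to Cox proportional hazard ratios (and 95% CIs"), with log-rank tests between curves. No endpoint is excepted. Competing risks appear once in the section: "Cause-specific mortality will also be analyzed using competing risks methods".

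The endpoints in Section 2 differ in which deaths they count:

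- The primary endpoint reads: "composite of CV death, MI, stroke or coronary revascularization in patients completing participation in the FOURIER OUTCOMES trial over a period of up to 5" (the unit being years from the close of the parent trial). CV death is an event, so only non-CV death can preclude it. The same holds for the secondary composite of CV death, MI and stroke.
- A secondary objective takes the "individual components of the primary endpoint and any other cardiovascular hospitalizations". For MI, stroke, coronary revascularization and hospitalization taken singly, any death that is not itself the event precludes it.
- Another covers the "long-term effect of evolocumab treatment on amputation and peripheral revascularization". Any death precludes these.

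Section 9.2 does not say how precluding deaths are handled in the curves and does not promise a 5-year incidence read from them. It leaves expanded detail to a separate SAP, which is not at hand.

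**The concern.** A participant who dies of a cause outside the endpoint can no longer have the event. A Kaplan-Meier analysis can only count that death as an event, which contradicts the endpoint definition, or censor it. Censoring treats the person as still able to have the event later. The resulting 1-KM then estimates risk in a setting where the competing deaths do not occur, and it exceeds the proportion of participants who actually have the event.

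The protocol acknowledges the issue for cause-specific mortality. The relative bias is just as large for the primary composite and larger for the non-fatal endpoints, where CV death competes as well, yet no such method is named for those.

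At stake are the absolute risks reported per arm. Section 1 gives weight to absolute risk when it summarises the statin follow-up evidence: "because of greater emerging absolute risk differences than those apparent immediately at trial end, the net clinical benefits estimated relative to treatment costs becomes more" favourable. Readers of this study are likely to take 5-year risks from the curves.

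**Working it through.** **Inputs from Protocol Section 9.1.** At least 10,000 participants; 5 years; a primary event rate of 5% per year ("with an assumed average post-trial event rate of 5% per annum for the primary endpoint excluding hospitalization for unstable angina pectoris (UAP")); CV death 4.94% against 3.8% over up to 5 years.

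**Assumptions, because the protocol gives no figure.** 5,000 per arm (1:1); constant hazards; complete 5-year follow-up apart from death; the 5% per year taken as the control-arm hazard; non-CV death 0.5 to 2% per year; a single non-fatal endpoint at 1 or 2% per year.

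**Step 1: the plan's own figure.** For 4.94% against 3.8% with 5,000 per arm, the difference is 0.0114. Its standard error (SE) is √[(0.0494×0.9506 + 0.038×0.962)/5,000] = 0.00409, so z = 2.79 and power = Φ(2.79 − 1.96), about 80%. The Schoenfeld formula with 5,000×(0.0494+0.038) = 437 events gives 80.1%. The stated 80% reproduces. For the primary endpoint, power is 99.9% for a 20% reduction and 95.8% for a 15% reduction, consistent with the stated figures of over 95% and over 90%. None of these depends on which curve is drawn.

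**Step 2: formulas.** With event hazard λ, competing-death hazard μ and T = 5:

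- 1-KM = 1 − exp(−λT)
- Cumulative incidence = λ/(λ+μ) × [1 − exp(−(λ+μ)T)]
- SE of 1-KM (Greenwood type) = exp(−λT) × √{λ/[n(λ+μ)] × [exp((λ+μ)T) − 1]}, n = 5,000

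**Step 3: primary composite.** λ = 0.05 gives 1-KM = 1 − exp(−0.25) = 22.12%. At μ = 0.01, cumulative incidence = (0.05/0.06) × [1 − exp(−0.30)] = 21.60%.

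| Non-CV death per year | Cumulative incidence | Overstatement (points) | Relative | In SEs |
|---|---|---|---|---|
| 0.5% | 21.86% | 0.26 | 1.2% | 0.4 |
| 1% | 21.60% | 0.52 | 2.4% | 0.9 |
| 1.5% | 21.34% | 0.78 | 3.6% | 1.3 |
| 2% | 21.09% | 1.03 | 4.9% | 1.7 |

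The SE is about 0.59 to 0.60 points throughout.

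**Step 4: single non-fatal endpoint.** The plan's CV death risk gives a hazard of −ln(1 − 0.0494)/5 = 1.01% per year. Adding non-CV death of 0.5, 1 or 2% per year gives all-cause death of about 1.5, 2 or 3% per year.

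- Endpoint at 1% per year: 1-KM is 4.88%, against 4.70%, 4.64% or 4.53%. The overstatement is 0.18, 0.24 or 0.35 points (3.8%, 5.1% or 7.7% relative).
- Endpoint at 2% per year with all-cause death of about 2% per year: 9.52% against 9.06%, or 0.46 points (5.0% relative). With the plan's CV death rate alone competing: 9.52% against 9.28%, or 0.23 points.

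**Step 5: where the protocol already applies the remedy.** For CV death, with 1% per year non-CV death, 1-KM is 4.94% against 4.82%: 0.12 points, or 2.5% relative. That is the same relative size as for the primary composite (2.4%) and half that for a non-fatal endpoint (about 5%).

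**Step 6: treatment contrast.** At HR 0.85 and 1% per year non-CV death, the active arm has 1-KM 19.14% and cumulative incidence 18.69%. The between-arm difference is 22.12 − 19.14 = 2.98 points by Kaplan-Meier and 21.60 − 18.69 = 2.91 by cumulative incidence, a shift of 0.07. Over 0.5 to 2% per year the shift at HR 0.85 runs from 0.03 to 0.13 points. At HR 0.80 and 2% per year it is 1.03 − 0.85 = 0.18. The SE of the difference is about 0.8 points.

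**The case against.** The strongest reply is that the estimator for each curve is SAP material, and the protocol defers detail to a SAP that may already settle this. It is fair that the unseen SAP may do so. But the protocol is not silent: it names Kaplan-Meier for time-to-event data without exception, and a SAP using another estimator would be departing from that sentence.

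A reader might infer that the protocol restricts competing-risks methods to mortality. It does not: cause-specific mortality will *also* be analysed that way, and nothing excludes wider use. A reader might also infer that the published 5-year incidences will be wrong. That goes too far, because the protocol promises no such estimate, and it allows other displays of the long-term trajectory, such as landmark analysis and conditional probability plots. The bias arises only if 1-KM is read as incidence.

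Nor do the documents support a claim that the treatment effect is distorted. Censoring competing deaths is valid for the cause-specific hazard ratio and the log-rank test, and Kaplan-Meier curves match that comparison. The Section 1 remark concerns differences between arms and summarises statin evidence, and such differences hardly move here. The objectives in Section 2 ask for treatment effects, not per-arm incidence.

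Finally, the ratio to the standard error depends on the large sample and on assumed death rates. At 0.5% per year it is 0.4, so one cannot say that the bias generally matches or exceeds the standard error.

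What remains is that the stated display does not estimate per-arm incidence for most endpoints, that the direction of the error is certain, and that the protocol already names the remedy for a neighbouring family of endpoints.

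**Conclusion.** The point holds as a minor one about reported absolute risks. Where an endpoint leaves out some or all deaths, 1-KM read as per-arm 5-year incidence is modestly too high. For the primary composite the excess is about 0.3 to 1.0 points on 22% (1 to 5% relative, 0.4 to 1.7 SE). For a non-fatal endpoint at 1% per year it is about 4 to 8% relative. These sizes rest on assumed non-CV death of 0.5 to 2% per year, 5,000 per arm and constant hazards; the direction does not. The bias is nearly proportional in the two arms, so the risk difference moves by about 0.1 point (0.18 at the extreme of the range examined). Hazard ratios, log-rank tests and stated power stand, and the main inference is not in question.

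**What to change.** In Section 9.2, extend the competing-risks sentence beyond mortality:

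- For every endpoint that does not include all-cause death, estimate per-arm incidence curves and 5-year risks by Aalen-Johansen cumulative incidence, by original assignment.
- For the primary composite and the composite of CV death, MI and stroke, the competing event is non-CV death.
- For MI, stroke, coronary revascularization, other CV hospitalization, amputation and peripheral revascularization, the competing event is any death not counted as the endpoint.
- Keep the cause-specific Cox hazard ratio and log-rank test as the treatment comparison, and Kaplan-Meier for all-cause death.

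The cost is one sentence and a change of estimator in the figures. No new data are needed: Section 5.1 collects CV and non-CV deaths, and Section 8.1 sends all deaths to central adjudication. The downsides are slightly lower reported incidences and less direct comparability with any Kaplan-Meier figures from the parent trial; Kaplan-Meier versions can be kept as a supplement. Settling it before the first interim analysis avoids replacing curves later. If the SAP already specifies this, only the protocol sentence needs aligning.

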3.2 Study Enrolment

Subjects who completed the FOURIER OUTCOMES trial (defined as attendance at close-out visit irrespective of treatment compliance) will be approached by FOURIER OUTCOMES site investigators and asked about their interest in taking part in this trial. Contact details of those interested in taking part will be forwarded to the national co-ordinating center (NCC), who will contact participants to confirm consent.

Assent: Confirmation by site staff of the participant's agreement to be contacted for consent by the NCC will be provided to the NCC.

Consent: Participation will require a specific consent by each participant to allow on-going contact to be made periodically to achieve follow-up for a total of approximately 5 years from completion of the FOURIER OUTCOMES trial. Telephone consent may be acceptable if allowed by local

regulations and approved by the Ethics Committee. Additionally, approval to hold each participant's contact details (in addition to contact details for at least one relative not living with the participant) and details of treating physician(s) will be sought to facilitate reliable on-going follow-up, and signed authorization for study staff to seek supplementary information and source documentation about health events will be collected. Participants will provide details of the preferred mode of communication (SMS, email, letter, phone) at the time of consent. Personal data identifying trial participants will be held securely solely at each NCC for the purpose of follow-up.

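### Trajectory analyses run from randomisation in LEGACY entrants only, so in-trial deaths cannot appear, and the main tests have no stated time origin

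*Protocol*

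**What the plan says.** Protocol section 9.2 defines the analysis set: "Analyses will include all participants who entered the FOURIER LEGACY study in participating countries". It says that event data will be analysed by original allocation, as intention-to-treat, with Kaplan-Meier curves, Cox models and log-rank tests. That paragraph states no time origin.

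A later paragraph of 9.2 adds: "Separate analyses examining effects post study close will be performed to evaluate the trajectory of effects long-term". It gives "landmark analysis and conditional probability plots" as example methods and places the work "again by original treatment assignment, among the FOURIER LEGACY study cohort from the time of randomization".

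Section 3.2 limits entry to FOURIER completers, "defined as attendance at close-out visit irrespective of treatment compliance", who then give a specific consent for LEGACY. Section 3.1 admits completers whatever non-fatal events they had in FOURIER.

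The objectives in section 2 cover up to 5 years after FOURIER ended. Section 9.1 sets the power "to detect an additional 20% proportional event reduction accruing post-trial". Section 5.2 undertakes to find the causes of death of people who died between FOURIER close-out and the start of LEGACY.

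**The concern.** The cohort is defined by something that happens after randomisation, namely being alive at close-out and consenting later. The clock in the trajectory sentence nevertheless starts at randomisation. The stretch from randomisation to consent is immortal time. CV, CHD, non-CV and all-cause death, all of them secondary objectives, can show no event in it. The composite is distorted in a different way, because it keeps in-trial non-fatal events and loses the fatal ones. Removing randomised patients because they died is not intention-to-treat from randomisation.

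The sentence also works against itself. Its stated purpose is the effect after study close, but its origin brings in the trial period, for which section 1 already reports a benefit. The main Cox and log-rank paragraph is silent on origin, so randomisation is the only start of follow-up that 9.2 names for an event analysis. If that origin were carried into the main test, the known in-trial benefit would contribute to a result presented as a legacy effect.

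**Working it through.** **1. The plan's own power, on post-trial events (9.1).** Inputs: 10,000 participants, 5% per year, 5 years, two-sided 0.05. Assumption: 1:1 allocation, 5,000 per arm. Schoenfeld: power = Φ(√D/2 × |ln HR| − 1.96), with D the expected number of events.
- 20% reduction: D = 5,000 × (0.25 + 0.20) = 2,250; √2,250/2 × 0.2231 = 5.29; power above 99.9% (plan: over 95%).
- 15% reduction: D = 5,000 × (0.25 + 0.2125) = 2,312; √2,312/2 × 0.1625 = 3.91; power 97.4% (plan: over 90%). With exponential event times, D = 2,063 and power 95.8%.
- CV death, 4.94% against 3.8%: 79.6% by two proportions (plan: 80%).

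The stated power therefore reproduces when events are counted after close-out.

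**2. Deaths that cannot appear.** Section 9.1 plans 4.94% CV death over 5 years, or 4.94/5 = 0.99% per year. Applying that rate to the trial period (an assumption) gives 0.0099 × 2.2 years × 5,000 ≈ 109, about 110 CV deaths per 5,000 placebo patients. In LEGACY entrants followed from randomisation this count is zero by definition. The gap between close-out and consent adds more, but the protocol does not give its length, so no figure is put on it.

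**3. If the main test were read as starting at randomisation.** Suppose evolocumab has no effect after close-out (post-trial HR 1.00, 5% per year, 5 years). In-trial HR: 0.85 or 0.80, the two reductions reported in section 1, which belong to two different composites. In-trial rate of countable (non-fatal) events: assumed 2% to 5% per year. The upper end equals the parent placebo rate in 9.1 (11.3%/2.2 = 5.1% per year), which includes fatal events and so is generous.

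Overall ln HR ≈ [E_in × ln(HR_in) + E_post × 0]/(E_in + E_post). Chance of p<0.05 = Φ(z − 1.96) + Φ(−z − 1.96), where z = √(E_in + E_post)/2 × |overall ln HR|.

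| In-trial rate per year | In-trial HR | E_in | E_post | Overall HR | Chance of p<0.05 |
|---|---|---|---|---|---|
| 2% | 0.85 | 399 | 2,124 | 0.97 | 10% |
| 2% | 0.80 | 388 | 2,126 | 0.97 | 14% |
| 3% | 0.85 | 592 | 2,081 | 0.96 | 15% |
| 3% | 0.80 | 576 | 2,084 | 0.95 | 24% |
| 4% | 0.85 | 782 | 2,039 | 0.96 | 22% |
| 4% | 0.80 | 761 | 2,044 | 0.94 | 36% |
| 5% | 0.85 | 967 | 1,998 | 0.95 | 30% |
| 5% | 0.80 | 942 | 2,004 | 0.93 | 49% |

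With the origin at close-out the corresponding figure is the nominal 5%.

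**4. Does conditioning on survival bias the post-trial contrast itself?** A log-normal frailty shared by in-trial death and post-trial events was used, with assumed in-trial mortality of 2% to 10%, in-trial death HR 0.8 and frailty SD 0.5 to 1.5. A true null then gives a post-trial risk ratio of 1.001 to 1.031, slightly against evolocumab. With equal in-trial mortality in the two arms it is 1.000.

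**The case against.** A reader might infer that the primary test itself starts at randomisation. The protocol does not say so. The hypothesis in section 1, the objectives in section 2 and the power in 9.1 all point to events after FOURIER, and the sentence on origin covers separate analyses. A landmark set at close-out would remove the in-trial benefit from them. Section 9.2 also foresees time-partitioned regression if proportionality fails, and the SAP, which is not shown, may fix the origin. This stands: mixing in the primary test is a risk left open by silence, not a stated plan, and step 3 is conditional on that reading.

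A reader might also infer that survivor selection could manufacture a legacy benefit. Step 4 does not support this: the effect is small, runs towards harm, and is unavoidable in any cohort that consents after the trial.

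Nor does 9.2 say that its comparison of contributors with non-contributors is pooled over arms. It only fails to name a comparison within arm.

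None of this answers the core point. The stated set and the stated origin together give mortality curves with an empty in-trial segment. Neither a landmark nor partitioned regression puts the missing deaths back. Moving the origin to close-out is not a full cure either, because entrants must still survive from close-out to consent.

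**Conclusion.** The point holds for the trajectory analyses as written. In LEGACY entrants followed from randomisation, all death endpoints have zero in-trial events by construction and the composite lacks its fatal in-trial part. The intention-to-treat label does not fit either. At the plan's own rate about 110 CV deaths per 5,000 placebo patients over 2.2 years are missing, assuming that the planned post-trial rate applies in the trial.

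For the primary test the finding is narrower: the time origin is unstated, and the one origin that 9.2 names conflicts with the objectives and the power. If that origin were adopted, a null post-trial effect would give an overall HR of about 0.93 to 0.97 and p<0.05 in about 10% to 49% of trials. This range rests on 1:1 allocation, an in-trial non-fatal rate of 2% to 5% per year and an in-trial HR of 0.85 or 0.80 among entrants. It should be quoted only with those conditions.

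**What to change.** Amend section 9.2 before any interim analysis:

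1. State that the primary and secondary tests count first events after FOURIER close-out (last FOURIER contact). For death, either treat entrants as at risk only from LEGACY entry (delayed entry), or include the deaths between close-out and the start of LEGACY. Section 5.2 already seeks those deaths, but the people concerned lie outside the present analysis set, so the second option means widening it.
2. Run any analysis with time zero at randomisation in all participants randomised in the participating countries. Count FOURIER deaths and events, handle the gap in the same way, and show the in-trial and post-trial HRs separately.
3. Report LEGACY entry by arm and compare entrants with non-entrants within arm. Optionally add a sensitivity analysis weighted by the inverse probability of entry, modelled on baseline and in-trial event data.

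The cost is wording and modest programming, since 9.2 already brings the FOURIER data into the follow-up database. The weighting adds some variance, in the sensitivity analysis only. Counting events after close-out leaves the stated power for the primary endpoint intact (step 1). Delayed entry would drop any deaths before consent from the risk set, as the present analysis set already does.
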